4.6 BG Analysis Eligibility (BGE)

Eligibility for BG analysis will be defined as an eligible subject that has at least 20 days of BG measurements prior to Visit 1. Analysis of BG data will be performed on both FAS and ITT populations, excluding subjects not eligible for BG analysis.

5 STATISTICAL ANALYSES

5.1 Study Populations

The number and percentage of families within each analysis population and treatment group will be summarized overall and by exclusion reason from each population. The denominator for each population will be the Safety Population.

5.2 Demographics and Baseline Characteristics

Demographic and baseline characteristics will be summarized descriptively for each analysis population and treatment group. Categorical variables will be summarized via counts and percentages, and continuous variables via mean, standard deviation, and range. Demographic and Baseline characteristics will be presented for both FAS and ITT populations.

5.2.1 Parent/Caregiver of Child/Adolescent with Diabetes

Variables from the Parent/Caregiver Pre-Questionnaire or derived baseline characteristics to be summarized are:

- Age
- Gender, race, ethnicity
- Marital Status
- Highest level of education
- Current Employment

5.2.2 Child or Adolescent with Diabetes

Variables from the Baseline Visit for the Child or Adolescent with diabetes or derived baseline characteristics to be summarized are:

- Age (continuous) and categorical: (8 - 11, 12 - 18) at informed consent
- Gender, race, ethnicity
- Height, weight, BMI
- Duration of diabetes
- Duration of this therapy
- Current type of insulin
- Average total daily basal dose, average total daily bolus dose, average number of boluses/day, and whether or not a bolus calculator is used.
- Average frequency of SMBG use
- HbA1c

5.3 Diabetes Management and Diabetes Related Absences

Diabetes management and diabetes related absences will be summarized descriptively for each analysis population and treatment group. Categorical variables will be summarized via counts and percentages, and continuous variables via mean, standard deviation, and range.

Demographic and Baseline characteristics will be presented for both FAS and ITT populations.

5.3.1 Parent/Caregiver of Child/Adolescent with Diabetes

Variables from the Parent/Caregiver Pre-Questionnaire to be summarized are:

- Communication method and frequency parent to child
- Primary school staff contact for diabetes communication with parent
- Communication method and frequency parent to school staff
- Number of diabetes related absences in last 3 months due to doctor appointments, illness or other

5.3.2 Child or Adolescent with Diabetes

Variables from the Baseline Visit for the Child or Adolescent with diabetes to be summarized are:

- Prior use of CGM, DMS, or Diabetes management app
- Diabetes management responsibility
- Communication method and frequency child to parent
- Number of diabetes related absences in last 3 months due to doctor appointments, illness or other

5.4 Family Disposition

The number and percent of study subjects who discontinue early along with the reasons for discontinuation will be summarized by study population and treatment group. The number and percent of study subjects present at each study visit will also be presented.

5.5 “Efficacy” Analyses

5.5.1 Primary Analysis

The primary analysis variable – change from baseline in PAID – Parent (YP or TP), will be summarized by treatment group at 6 months via descriptive statistics and will be analyzed for treatment group differences by an analysis of covariance (ANCOVA). The model will include the independent variable – change from baseline in PAID, and the baseline covariates of baseline PAID, age of child, and duration of diagnosis. Additionally, the results of a 2-sample

t-test comparing the group means will also be provided. If deviations from normality are significant, non-parametric methods, such as Wilcoxon Rank Sum Tests will be employed. The primary analysis population will be the FAS population.

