2.1 Study Design Overview

This is a prospective, interventional, multi-center, post-market, 6-months, cluster randomized study, conducted in the US. In order to maintain a true control group for comparison, the investigational sites will be randomly assigned to one of the following treatments:

- Interventional Group ACCU-CHEK® Connect Diabetes Management System
- Control Group Usual care: Continued use of subjects' current diabetes devices

[figure not shown]

Figure 1 Study Design

Between 150 - 200 children with diabetes will be included in the clinical study and the duration of participation is 6 months for each subject. A cluster of 10-20 children is expected to enroll at each investigational site.

All subjects recruited by an Interventional Site will be provided with an ACCU-CHEK[®] Connect DMS (and up to one additional meter to keep at school), trained in the system's use, and asked to use this system for the following 6 months.

All subjects recruited by the Control site will continue to use their current diabetes management system.

All parents/caregivers independently of the age of their child are also part of the study, and will complete questionnaires about diabetes related stress, system use and other aspects of diabetes.

Furthermore, the health care providers (investigators and study staff) as well as school staff will also be asked to assess their preference in comparison to previously used systems. In order to obtain data prior to study start self-monitored blood glucose (SMBG) data from all subjects will be downloaded at Baseline using Diasend – for the data transfer to the eCRF

During the study the Control sites will continue to download data using Diasend whereas data download at Interventional sites will be managed by ACCU-CHEK® Connect DMS.

Control sites will continue to use data analysis methods according to their current practice for making therapy decision throughout the study. No change in behavior should be introduced by the study in this group and therefore they will not use data downloads via Diasend for therapy decisions, if this is not currently their practice, but they might need to perform downloads via Diasend for eCRF transfer only.

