4.2 Secondary Objectives

The secondary objectives of this study are to assess the changes in the following measures after 3 and 6 months utilization of the ACCU-CHEK® Connect DMS compared with usual care:

- Change in diabetes-related distress among parent/caregiver. (PAID-C & T Parent Questionnaires) at 3 months compared to Baseline
- Change in diabetes-related distress among school-age children with diabetes. (PAID-C & T Child Questionnaires) at 3 and 6 months
- Change in perceived family conflict among school-age children with diabetes and parent/caregiver. (DFCS-parent and DFCS-youth Questionnaire) at 3 and 6 months
- Change in affect toward blood glucose monitoring (BGM) among school-age children with diabetes and parent/caregiver. (BGMC-parent and BGMC-youth Questionnaire) at 3 and 6 months
- Changes in glycemic control:
 - o HbA1c
 - Percentage in Glucose Target Range
 - Glycemic Variability
 - o Hypoglycemia

Intervention Group Only at 6 months:

- Use of, Preference, Satisfaction with the ACCU-CHEK Connect DMS
 - Parent/caregiver(s)
 - o children/adolescents with diabetes
 - School staff
 - o Healthcare Provider (investigator and study staff)

5 Selection of Subjects and Investigators

Investigational sites will be recruited from pediatric endocrinology practices in the US. When the complete cohort of sites have been selected to participate, a random assignment of each site to intervention or control treatment groups will be performed and communicated to the primary investigators.

Subjects will be identified and recruited from the Investigator's (pediatric endocrinology practices) established subject population or from respective group practices using the inclusion criteria; see Section 6.

If a subject and his/her parents/caregivers agree to consider participation in the study, the parents/caregivers will be informed verbally and in writing by means of review of the Informed Consent Form. Time for the possibility to ask questions to authorized study staff will be provided prior to obtaining signatures.

If a subject and his/her parents/caregivers decide to participate, the parents/caregivers shall sign the current IRB approved informed consent form before any study-related procedures;

Children with diabetes will be informed in language according to their age, and asked to sign the assent form before any study-related procedures.

Please refer to Section 12.2.

6 Study Population

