2 STUDY DESIGN

2.1.1 Study Population

This is a prospective, interventional, multi-center, post-market, 6-months, cluster randomized study, conducted in the US. Eight (8) to thirteen (13) pediatric endocrinology centers across the US are to be randomly assigned to one of 2 treatment groups in a 1:1 allocation. The groups are A) Intervention: using the ACCU-CHEK® Connect Diabetes Management System, or B) Control: Continued use of subjects' current diabetes devices. To be eligible for the study, children must have a diagnosis of T1D for ≥ 3 months, currently managed with multiple daily insulin injections, 6-18 years of age, attending full day school K-12 grades, able to provide

SMBG data for a minimum of 1 month prior to study start, and using a Smartphone capable of downloading the ACCU-CHEK Connect System App (or able to use a Smartphone that is provided). Parents/caregivers and adolescents (18 yrs old) must provide informed consent and children 7-17 yrs old must provide child assent. Parent/caregiver of study subjects must also be using a Smartphone and be able to receive SMS/MMS messages.

Children/adolescents will be excluded if they are on CSII therapy or are planning to transition to CSII during the study, are CGM users or use a remote data sharing system/device such as NightScout, DexCom Share, or Medtronic Connect, are pregnant, or are diagnosed with any clinically significant condition, or have requirements for chronic steroids in adrenal suppressive doses, immune-modulatory medications, or chemotherapy. Subjects will be excluded if they or their parent/caregiver have visual impairment preventing the complete use of the ACCU-CHEK Connect system or if the parent/caregiver is directly involved in the conduct of the study or design of the protocol.

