2.1.2 Sample size justification

Change from baseline in PAID-C & T parent, the primary endpoint was used to estimate the sample size requirement for the study. A sample size of 75 per group would be sufficient, with a power of 80% to detect a treatment effect of 0.460 with a significance level of 0.05. Given assumptions of SD of 5 to 16, the sample size would be able to detect treatment group differences of 2.3 (SD=5) to 7.4 (SD=16.0). 100 subjects per group will be enrolled to accommodate attrition.

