5.5.2 Secondary Analyses

Secondary objective variables collected in both treatment groups will be summarized by group utilizing descriptive statistics. Statistical comparisons between groups of continuous variables will utilize the same ANCOVA method discussed above substituting the baseline value of the independent parameter, as well as 2-sample t-tests or non-parametric Wilcoxon Rank Sum tests. The following variables will be analyzed:

1. Change from baseline in PAID-parent (YP and TP) at 3 months
2. Change from baseline in DFCS – parents at 3 and 6 months
3. Change from baseline in BGMC-parents at 3 and 6 months
4. Change from baseline in PAID-child (Y or T) at 3 and 6 months
5. Change from baseline in DFCS-child at 3 and 6 months
6. Change from baseline in BGMC-child at 3 and 6 months
7. Changes from baseline in glycemic control (HbA1c, % BG in target, mean BG, SD BG, and % hypoglycemic events) at 3 and 6 months

Secondary objective variables collected in the Intervention treatment group only (ease of use, satisfaction and preference for using the ACCU-CHEK® Connect DMS System by parents, children, school staff, and HCP) will be summarized by question utilizing descriptive statistics of the numerical scale (mean, standard deviation, range and 95% CI) and the distribution of values (number and % of respondents at each level of response).

All secondary analyses will be performed on both the FAS and ITT populations.

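### Sites are randomised, but the primary ANCOVA treats families as independent, so the two-sided 5% level is exceeded if families within a site are positively correlated

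*SAP*

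**What the plan says.** Both documents describe a cluster-randomised trial. Protocol 2.1 says that "the investigational sites will be randomly assigned to one of the following treatments", and Protocol section 5 repeats that "a random assignment of each site to intervention or control treatment groups will be performed". SAP 2.1.1 gives the number as 8 to 13: "pediatric endocrinology centers across the US are to be randomly assigned to one of 2 treatment groups in a 1:1 allocation". On cluster size, Protocol 2.1 says: "A cluster of 10-20 children is expected to enroll at each investigational site".

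SAP 5.5.1 analyses the 6-month change in parent PAID by ANCOVA, "and the baseline covariates of baseline PAID, age of child, and duration of diagnosis". It adds a two-sample t-test and, if normality fails, "non-parametric methods, such as Wilcoxon Rank Sum Tests will be employed". SAP 5.5.2 says that the secondary comparisons "will utilize the same ANCOVA method discussed above substituting the baseline value of the independent parameter", again with t-tests or Wilcoxon tests.

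The sample size in SAP 2.1.2 is 75 per group with 80% power "to detect a treatment effect of 0.460 with a significance level of 0.05"; Protocol 11.1 adds that the test is two-sided. Enrolment of 100 per group is explained by attrition alone. The name of the primary model is blank in the protocol synopsis and in Protocol 11.4, so this point rests on the SAP, whose sentence is complete. No readable text in either document adds a site adjustment, an ICC or a design effect.

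**The concern.** Each site contributes families to one arm only. Any difference between sites in how parental distress changes therefore enters the treatment contrast directly. A family-level ANCOVA estimates its standard error from the scatter among families and counts about 150 independent observations, although only 8 to 13 units were randomised. If families at a site are positively correlated after covariate adjustment, the standard error is too small and the test rejects too often.

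Nothing in the documents supports a correlation of zero. Families at one site are trained by that site at Visit 1 (Protocol 7.8), and its team agrees therapy changes with them during follow-up (Protocol 7.4). Adjusting for baseline PAID does not remove influences that act after baseline. These facts show that zero is not established; they do not show how large the correlation is.

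At stake is the validity of the trial's one primary test: a p-value just below 0.05 could not be taken at face value. The documents state no significance level for the secondary endpoints. There, p-values are too small to the extent that each endpoint is correlated within site.

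**Working it through.** **1. The plan's own figure.** Inputs (Protocol 11.1, SAP 2.1.2): 75 per group, standardised effect 0.460, two-sided 0.05. The noncentrality is 0.46 × √(75/2) = 2.817 on 148 degrees of freedom, which gives power of 79.9%. The detectable differences also reproduce: 0.46 × 5 = 2.3 and 0.46 × 16 = 7.36. The calculation therefore uses the formula for individual randomisation, with a design effect of 1.

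**2. Actual level of the planned test.** With m analysed families per site, DE = 1 + (m − 1) × ICC. The actual two-sided level is approximately 2 × [1 − Φ(1.96/√DE)]. Assumptions: about 150 analysed families, so m = 150/8 = 18.75 or 150/13 = 11.54, and an ICC (after covariates) of 0 to 0.05.

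| Sites | ICC | DE | 1.96/√DE | Level |
|---|---|---|---|---|
| 8 | 0.01 | 1.178 | 1.806 | 7.1% |
| 8 | 0.05 | 1.888 | 1.427 | 15.4% |
| 13 | 0.01 | 1.105 | 1.864 | 6.2% |
| 13 | 0.05 | 1.527 | 1.586 | 11.3% |

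**3. Simulation of the SAP ANCOVA.** There were 20,000 runs per null setting (Monte Carlo standard error about 0.15 points at 5%). The covariates explained 0, 30% or 50% of the variance, or 30% with the covariates themselves clustered (ICC 0.1). Ranges are over these settings.

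| Sites | ICC 0 | 0.01 | 0.02 | 0.05 |
|---|---|---|---|---|
| 8 (19 each) | 4.9-5.3% | 6.8-7.3% | 9.0-9.3% | 15.3-15.5% |
| 13 (11-12 each) | 4.7-5.0% | 5.9-6.2% | 7.1-7.6% | 11.0-11.4% |

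The inflation hardly depends on how strong the covariates are.

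**4. The t-test and Wilcoxon.** At 8 sites and ICC 0.05 the t-test gives 15.6%, 12.7% and 10.6% at R² of 0, 0.3 and 0.5. The Wilcoxon test gives 15.1%, 12.4% and 10.2%. With clustered covariates at R² 0.3 the values are 18.4% and 18.0%. Neither test is a safeguard.

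**5. A test at the level of randomisation.** Slopes of baseline PAID, age and duration were estimated within site. Adjusted site means were then compared by a t-test on sites-minus-2 degrees of freedom. Type I error was 4.6-5.4% over 80 null settings, which also covered 10 sites and ICC up to 0.10. For a true effect of 0.46 the mean estimate was 0.458-0.464, with 94.6-95.5% coverage of the 95% interval.

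**6. Power of that test at effect 0.46.** If the covariates explain nothing, the variance of the difference is v = [ICC + (1 − ICC)/m] × (1/k₁ + 1/k₂), where k₁ and k₂ are the sites per group, and the noncentrality is 0.46/√v.
- 8 sites, ICC 0.01: v = (0.01 + 0.99/18.75) × (1/4 + 1/4) = 0.0314. The noncentrality is 2.596 against a critical value of 2.447 on 6 degrees of freedom, so power is 58.5% (simulated 59.1%).
- 13 sites, ICC 0.01: v = (0.01 + 0.99/11.54) × (1/6 + 1/7) = 0.02965. The noncentrality is 2.671 against 2.201 on 11 degrees of freedom, so power is 68.2% (simulated 67.2%).
- ICC 0.05: 40.7% with 8 sites and 54.5% with 13 (simulated 39.7% and 54.1%).

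If the covariates explain 30%, simulated power is 73-82% at ICC 0.01 and 53-69% at 0.05 (8 to 13 sites).

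**The case against.** The best counter-argument is that the size of the problem is assumed. The documents give no ICC; at zero the planned test holds its level, at 0.01 the excess is one to two points, and nothing in the text points to 0.05. That is right about the size. It does not rescue the plan, because the stated level holds only at a correlation that is effectively zero, and the plan gives no reason to expect that.

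A second objection concerns the 8-site figures. With 150 analysed families, 8 sites need about 19 each. If at most 20 enrol per site and a quarter are lost, as 75 analysed of 100 enrolled implies, about 15 per site remain. The level is then 6.6% at ICC 0.01 (DE 1.14) and 13.3% at 0.05 (DE 1.70). Power of the site-mean test falls to about 51% and 37%. So the upper 8-site levels require low drop-out; they are reachable within the planned 150-200 enrolled and 10-20 per site. The conclusion is the same either way.

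Third, comparing site means is only one valid choice, and equal site weights change what is estimated when sites differ in size. This stands: the SAP should state the weighting, and a suitable mixed model is also acceptable.

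**Conclusion.** The concern holds and should be fixed before the analysis. The omission is certain from the SAP text: sites are randomised, and none of the planned tests takes account of site. The consequence is conditional. The primary test exceeds two-sided 5% whenever the covariate-adjusted ICC is above zero. Under the stated assumptions the excess is small at ICC 0.01, and at 0.05 the level is two to three times nominal. The ICC, the covariate strength and the roughly 150 analysed families are assumptions; the number of sites, the allocation and the effect size come from the documents.

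**What to change.** In SAP 5.5.1, pre-specify one cluster-aware primary test that is valid for 8 to 13 sites. For example:

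- Estimate the slopes of baseline PAID, age of child and duration of diagnosis within site, using site indicators in this step only.
- Form each site's adjusted mean change, and compare the site means between groups by a two-sided t-test with sites-minus-2 degrees of freedom.
- State that sites are weighted equally, and take the estimate and confidence interval from the same step.

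Two variants of the slope step do less well. Slopes fitted without treatment group keep the level (4.7-5.4%) but shrink the estimate (0.433-0.455 for a true 0.46); the reported estimate must then come from a model that includes treatment group. Slopes taken from the family-level ANCOVA give 5.1-6.3% and are not recommended.

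A random-site-intercept model with the Kenward-Roger correction is an acceptable alternative. Its simulated type I error was 1.0-5.0%, and it was conservative at 8 sites (1.0-1.2% at ICC 0, 3.1-3.5% at 0.05). Do not put a fixed site effect in the treatment model, because site is nested in treatment group.

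Use the chosen method in SAP 5.5.2 with each endpoint's own baseline value, and report the family-level t-test and Wilcoxon as descriptive only. In the same edit, name treatment group as the independent variable and the change score as the dependent one; SAP 5.5.1 now calls the change score independent and does not list treatment group.

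The direct cost is SAP wording and a little code, since the subject ID already carries the site number (Protocol 13.1.1). The real cost is power: SAP 2.1.2 should restate its 80% with an assumed ICC, and rewording cannot make up the shortfall.

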11.1 Null Hypothesis and Sample Size Calculation

The primary outcome variable is change from baseline in PAID-C & T Parents at 6 months. A sample size of 75 patients per group will have 80% power (α =0.05, 2-sided) to detect a treatment effect size of 0.460. Given assumptions of common SD from 5-16, this sample size would be able to detect treatment group differences of 2.3 to 7.4, respectively. In order to account for possible drop-out prior to the 6 month endpoint, 100 subjects per group will be enrolled.

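### SAP 5.5.1 does not say whether, or on what check, a rank test supersedes the primary ANCOVA, and it names no deciding p-value

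*SAP*

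**What the plan says.** SAP 5.5.1 analyses the change from baseline to 6 months in the parent PAID score on the FAS. It names an ANCOVA with baseline PAID, child age and duration of diagnosis as covariates, and then a two-sample t-test as an additional result. The next sentence reads: "If deviations from normality are significant, non-parametric methods, such as Wilcoxon Rank Sum Tests will be employed".

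For the secondary endpoints, SAP 5.5.2 keeps the same ANCOVA and continues: "as well as 2-sample t-tests or non-parametric Wilcoxon Rank Sum tests".

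Protocol 11.4 plans a covariate-adjusted comparison of the change score, plus t-tests. It has no non-parametric fallback.

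The sample size rests on a difference in means. Protocol 11.1 states that 75 per group "will have 80% power (α =0.05, 2-sided) to detect a treatment effect size of 0.460", and: "Given assumptions of common SD from 5-16, this sample size would be able to detect treatment group differences of 2.3 to 7.4, respectively".

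**The concern.** The sentence in SAP 5.5.1 makes a method in the primary analysis section depend on the outcome data, and four things are left open:

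- the normality check itself: which test, at what level, and on the raw change or on the model residuals;
- the fallback method, since Wilcoxon is only an example;
- whether the fallback replaces the ANCOVA, replaces only the t-test, or is reported as well;
- which p-value decides the primary objective.

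If the fallback supersedes the ANCOVA, three things follow. The primary test is picked after the data are seen. The covariate adjustment for baseline PAID, age and duration goes, although the change score still subtracts baseline. And a rank-sum comparison does not test the mean difference used in the sample size. If the choice is settled only once several p-values are in hand, the nominal 5% level is no longer protected.

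**Working it through.** **1. The plan's own figure.** Inputs from Protocol 11.1: effect 0.460, two-sided alpha 0.05, power 80%, 75 per group.

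- n per group = 2 × (1.960 + 0.842)² / 0.46² = 74.2, so 75. This reproduces.
- Power at 75 by the normal approximation: 0.46 / √(2/75) = 2.817, and Φ(2.817 − 1.960) = 0.804. The exact t-test gives 0.799.
- 0.46 × 5 = 2.3 and 0.46 × 16 = 7.36, which are the stated differences.
- 75 / 100 leaves room for 25% attrition, consistent with "100 subjects per group will be enrolled to accommodate attrition".

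The calculation is therefore an unadjusted comparison of mean change, with the effect in SDs of change.

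**2. Closed form with normal data.** The documents give no baseline-to-6-month correlation ρ, so it is an assumption. With equal variances at both visits and SD of change 1, the ANCOVA residual SD is √((1 + ρ)/2). ANCOVA power is Φ(2.817 / residual SD − 1.960). For Wilcoxon on the change score, power is Φ(2.817 × √(3/π) − 1.960) = 0.786, whatever ρ is.

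| ρ | Residual SD | ANCOVA power | Wilcoxon power |
|---|---|---|---|
| 0.3 | 0.806 | 0.937 | 0.786 |
| 0.5 | 0.866 | 0.902 | 0.786 |
| 0.7 | 0.922 | 0.863 | 0.786 |
| 0.8 | 0.949 | 0.844 | 0.786 |

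If Wilcoxon replaced the ANCOVA outright under normality, the loss would be 0.844 − 0.786 = 0.06 up to 0.937 − 0.786 = 0.15.

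**3. Simulated two-stage rule.** Assumptions: 75 per arm, effect 0.46 SD of change, no clustering, baseline as the only covariate, Shapiro-Wilk on ANCOVA residuals at 0.05, and Wilcoxon on the change score if that check is significant.

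| Errors | ρ | ANCOVA power | Two-stage power |
|---|---|---|---|
| Normal | 0.5 | 0.901 | 0.896 |
| Normal | 0.7 | 0.850 | 0.846 |
| Skewed, gamma(4) | 0.5 | about 0.90 | about 0.82 |
| Skewed, gamma(4) | 0.7 | about 0.85 | about 0.82 |
| Heavy-tailed, t with 5 df | 0.5 | 0.888 | 0.850 |
| Heavy-tailed, t with 5 df | 0.7 | 0.855 | 0.862 |

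A second set of gamma(4) trials gave 0.906 against 0.837 (ρ = 0.5) and 0.859 against 0.838 (ρ = 0.7), so those rows carry an uncertainty of one to two points.

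The size depends on the shape of the errors. With more strongly skewed gamma(2) data (6,000 trials per scenario), power went from 0.930 to 0.849 at ρ = 0.3, from 0.902 to 0.862 at 0.5, and from 0.848 up to 0.873 at 0.7.

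**4. How often the check fires.** Tested on residuals, it fires in about 5% of trials with normal errors, 99% with gamma(4) and 70% with t on 5 df. Tested on the change score, it fires in about 75–90% with gamma(4) and 45–56% with t on 5 df. The unspecified choice of variable therefore matters.

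**5. Type I error.** In the set of 6,000 trials per scenario (normal, gamma(2), and t with 4 df; ρ from 0.3 to 0.7), the Monte Carlo standard error is √(0.05 × 0.95 / 6000) = 0.003.

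- ANCOVA alone: 0.042 to 0.055 in every distribution.
- Fixed two-stage rule: 0.046 to 0.054.
- Smaller of the ANCOVA and Wilcoxon p-values: 0.072 to 0.085. Across all simulation sets the figure is about 0.06 to 0.08.

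**The case against.** The strongest reply is that the rank test was never meant to touch the ANCOVA. The normality sentence directly follows the t-test sentence, and Wilcoxon is the rank counterpart of that t-test. SAP 5.5.2 keeps the ANCOVA and offers the t-test or Wilcoxon beside it. Protocol 11.4 has no fallback at all. This reading is reasonable, so a reader who infers that the SAP orders a switch away from the ANCOVA goes further than the text. But the sentence is unqualified and stands in the primary section, and ANCOVA is itself usually taught with a normal-errors assumption, so replacement is also a natural reading. That both can be held is the defect.

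Three other inferences are tempting and not supported:

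- **That baseline is discarded.** The outcome is a change score, so baseline is still subtracted; only covariate adjustment would go. The wording would also admit an adjusted rank method.
- **That the switch inflates type I error.** A rule fixed in advance does not do so visibly. Inflation needs a choice made after both results are known.
- **That the trial falls below its planned power.** At ρ of 0.5 and 0.7 the two-stage rule stays above 0.80 at the planned effect. What is lost is surplus, because 75 per group was computed for an unadjusted comparison.

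**Conclusion.** The point holds as an ambiguity in the primary analysis that should be removed: the SAP does not settle whether a rank test supersedes the ANCOVA, on what check, or which p-value counts. If it does supersede, the cost in the gamma(4) runs is about 8 power points at ρ = 0.5 and about 3 at 0.7. It is larger at lower correlation, and it is nil or a small gain in some skewed or heavy-tailed cases at 0.7. The test would also no longer match the mean difference that sized the trial. All of this rests on an assumed correlation, error shape and normality check, none of which the documents give, and it ignores clustering.

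The trigger also brings little benefit. At 75 per arm the ANCOVA kept its type I error close to 0.05 under every distribution tried.

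**What to change.** Delete the normality trigger from SAP 5.5.1 and state the hierarchy along these lines:

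> The sole primary test is the ANCOVA of the 6-month change in parent PAID (dependent variable) on treatment group, baseline PAID, child age and diabetes duration, whatever the distribution of the data. The two-sample t-test and a rank-based analysis, preferably covariate-adjusted, are prespecified sensitivity analyses and do not decide the primary objective.

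Use the same hierarchy in SAP 5.5.2, where the choice between t-test and Wilcoxon also has no rule. The rewrite also corrects the present model sentence in 5.5.1, which labels the change score as the independent variable and leaves treatment group out of the listed terms.

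The cost is SAP wording only, made before outcome data are examined. How to account for randomisation by site is a separate issue that this change does not resolve.
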